**December 2019**

**What is already known on this subject? And  
What does this study add?**

Video-assisted thoracic surgery (VATS) is usually performed with general anesthesia and single lung ventilation. However, performing thoracic surgery under awake regional anesthesia has several potential advantages including avoidance of airway trauma and ventilator dependence associated with endotracheal intubation, besides promoting enhanced recovery after surgery and shorter mean hospital stay.

**1.INTRODUCTION/ REVIEW:**

Non-intubated Video-Assisted Thoracoscopic Surgery (nVATS), requires an increased anesthesiological effort, accurate patient selection and rigorous planning of airway management in that a switch to general anesthesia and lung separation becomes necessary. Lung separation is obtained with the induction of a surgical pneumothorax, although emphysema and pleural adhesions can slow down the resulting lung collapse (*Deng et al., 2016*).

The reasons for preference of awake patient includes; preservation of diaphragmatic activity besides avoidance of several complications related to general anesthesia such as; deterioration in respiratory functions (like atelectasis, ventilator-induced lung injury, diminished functional residual capacity leading to difficult weaning from mechanical ventilation), impaired cardiac performance and reduced postoperative nausea and vomiting. Lastly, a diminished recourse to anesthetic drugs help the preservation of hypoxic pulmonary vasoconstriction (*Chen et al., 2012*).

The main aim of TEA is to block somatosensory and motor fibers between T1-8 while keeping spontaneous breathing. During procedure, TEA in nVATS patients provided a good preservation of pulmonary functions which are reflected in arterial blood gas values. This can be justified by the increase in diaphragmatic shortening and increased functional residual capacity (FRC). (*Sagiroglu et al., 2018*).

On the downside, paradoxical breathing (Pendelluft effect) can develop between the two lungs, increasing the risk of hypoxemia and hypercapnia, sometimes so evident to require a switch to general anesthesia, in 1% of patients. In most cases, hypercapnia resolves spontaneously, and postoperative PaCO2 is actually lower than after conventional anesthesia. Moreover, permissive hypercapnia can have positive results on the general outcome. Hypotension, due to the mediastinal shift that occurs during pneumothorax, is a potential issue, but it does not appear to be more relevant than under general anesthesia (*Pompeo et al., 2015*).

## 2.AIM/ OBJECTIVES:

The aim of this study is to investigate the feasibility and the effect of Thoracic Epidural Anaesthesia for awake thoracic surgery to speed up recovery in patients as well as avoiding the complications accompanying General Anesthesia with one lung ventilation.

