Patients in thoracic epidural anesthesia (TEA) group will pre-medicated using midazolam 3-4 mg intravenous (IV) and fentanyl 50 mcg IV. Then patients will placed in the setting position. Under aseptic precautions, skin infiltration with local anesthesia will be done using a 5ml syringe containing 5ml of 1% lidocaine. An epidural catheter will be inserted between T3—T4 and T4—T5 for thoracic procedures meeting the inclusion criteria. A test dose (5 ml) of 2% lidocaine will be given, followed by 15-20 ml of bupivacain 0.5% and 50 mcg of fentanyl. The objective is to achieve sensory and motor block between C7 and T7 levels. At this level diaphragmatic respiration is maintained. In case of persistent hemodynamic instability or persistent hypoxemia, the patients will be transferred to the other group.

Patients will receive general anesthesia (GA) as follows, after proper assessment of the airway and anticipation of difficult airway, all patients will receive premedication in the form of 3-4 mg midazolam IV, ranitidine 50 mg IV as H2 receptor antagonist, metoclopramide 10 mg IV and dexamethasone 4 mg IV as post-operative nausea and vomiting (PONV) prophylaxis. Start preoxygenation with 100% O2 on 8 L/min for 3 min via face mask. Induction of anesthesia with propofol (2mg/kg) and fentanyl (1 mcg/kg). Tracheal intubation and double endotracheal tube insertion will be facilitated with cisatracurium 0.1 mg/kg. and confirmation of it is position will made by fiberoptic bronchoscopy, Anesthesia will be maintained with isoflurane (1-2 %) and cisatracurium (0.05 mg/kg per dose). After the end of the operation, anesthesia will be discontinued, and extubation of the patient will be done after full neuromuscular recovery after reversal of muscle relaxant by neostigmine (0.05 mg/kg) and atropine (0.02 mg/kg).

Postoperative pain and opioid consumption will be assessed after regaining of sensation using the VAS. Post-operative analgesia will be offered in regular doses of Paracetamol 1gm IV every 6 hours for the following 48 hours. Rescue analgesia will be given when VAS  $\geq$ 3, in the form of an injection of Pethidine 50 mg diluted in 10ml normal saline 0.9%, to be given intravenously slowly over 10 min.

- **Measured outcomes**

- **Primary outcome:**

Perioperative changes in blood gases [ Time Frame: Immediately before operation, intraoperatively per hour, and postoperatively per 2 hrs till 24h ]

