Ratio of arterial oxygen tension to fraction of inspired oxygen (PaO2/FiO2), arterial carbon dioxide tension (PaCO2). Hypoxemia is defined as peripheral oxygen saturation (SpO2) < 92% on room air with a need for oxygen supplementation.

- **Secondary outcomes:**

- Postoperative pain using the Visual Analogue Scale (VAS), [ Time Frame: Postoperatively at 3h,12h and 24h ].
- Postoperative opioid (Pethidine) consumption [ Time Frame: Postoperatively during the 24h after regaining of sensation ].
- Hospital stay [ Time Frame: from day of operation to discharge; average, 5 days ]
- Perioperative changes in cardiocirculatory variables including heart rate (HR) and mean arteial pressure (MAP) [ Time Frame: Immediately before the operation, intraoperatively per hour, and postoperatively per 2 hrs till 24h ]
  - Bradycardia is defined as:  $HR \leq 50$  bpm
  - Hypotension is defined as a decrease in systolic blood pressure  $>20\%$  of basal.
  - Hypertension is defined as an increase insystolic blood pressure  $>20\%$  of basal.
- The onset of ambulence. Rate of occurence of falling after ambulence will be recorded in each group. [Time Frame: During the 24 hours after regaining of full motor power].
- Number of episodes of PONV [Time Frame: During the 24 hours postoperatively].
- **Statistical Analysis:** The collected data will be revised, coded and introduced to a PC using statistical package for social science (SPSS 15.0.1. for windows; SPSS Inc, Chicago, IL, 2001).
 

Data will be presented as mean and standard deviation (+- SD) for quantitative parametric data, median and range for quantitative non-parametric data and as numbers and percentage for qualitative data. Suitable analysis will be done according to the type of data obtained.  $P < 0.05$  will be considered significant.

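### Feasibility is the first stated aim but no outcome measures it, and if transferred patients are counted in Group B, Group A cannot show a failure for the two transfer triggers

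*Combined protocol and SAP*

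**What the plan says.** Section 2 (Aim/Objectives) puts feasibility first: the study is to "investigate the feasibility and the effect of Thoracic Epidural Anaesthesia for awake thoracic surgery".

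Under Measured outcomes in section 3, the primary outcome is "Perioperative changes in blood gases", made up of "Ratio of arterial oxygen tension to fraction of inspired oxygen" and arterial carbon dioxide tension. The secondary outcomes are pain score, pethidine use, length of stay, heart rate and arterial pressure, time to walking (with falls), and finally "Number of episodes of PONV".

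Under Study Interventions, the paragraph on the epidural technique ends: "In case of persistent hemodynamic instability or persistent hypoxemia, the patients will be transferred to the other group". The same part of the protocol uses the word group for the two randomised arms, A and B.

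The Statistical Analysis paragraph names no analysis population. On method it says only: "Suitable analysis will be done according to the type of data obtained".

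The Introduction shows that conversion was foreseen. It describes hypoxaemia and hypercapnia from paradoxical breathing as "sometimes so evident to require a switch to general anesthesia, in 1% of patients".

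**The concern.** There are two linked gaps.

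- **A stated aim has no measure.** Nothing on the outcome list is a completion, block-success or conversion rate, and no criterion for calling the technique feasible is set.
- **Patients who convert may leave the denominator.** Group A is defined by receiving the epidural as sole anaesthetic, and a converted patient no longer fits that description. If such patients are counted in Group B, those remaining in Group A are selected for not having met either trigger.

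A statement that the awake technique is feasible could then rest on a group from which some failures had been removed. The effect comparison suffers too. Transfer depends on haemodynamics and oxygenation after randomisation, and these are close to the primary outcome and one of the secondary outcomes. Moving such patients from A to B would tend to flatter A and burden B.

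**Working it through.** **The plan's own figure.** The only calculated figure is the power of 100% under Sample Size.

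- Inputs: mean changes of -3 (SD 1.5) and -6.5 (SD 1.83) mmHg; alpha 0.05, taken as two-sided.
- Difference: 6.5 - 3 = 3.5.
- Pooled SD: √((1.5² + 1.83²)/2) = √((2.25 + 3.3489)/2) = 1.673.
- Power at 20 per group: 99.9998% (99.9996% with the noncentral t); higher at 30 or 40.

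The stated power is reproduced. It concerns an oxygenation difference and says nothing about feasibility.

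**Group size.** Sample Size gives 40 per group and also 40 in total, which would be 20 per group with equal arms. Study Interventions gives 60 patients, 30 per group. These need reconciling, so 20, 30 and 40 are all carried below. The conclusion does not depend on which applies.

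**Effect of the counting rule.** Let n be the number allocated to Group A and x the number converted for the two named triggers. Success as randomised is (n - x)/n. Success after transfer is (n - x)/(n - x), which is 100% for any x below n. The documents give no expected x for this trial, so the values below are assumptions, shown for n = 30.

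| Conversions x | As randomised | After transfer | Group sizes after transfer (A / B) |
|---|---|---|---|
| 0 | 30/30 = 100% | 30/30 = 100% | 30 / 30 |
| 1 | 29/30 = 96.7% | 29/29 = 100% | 29 / 31 |
| 2 | 28/30 = 93.3% | 28/28 = 100% | 28 / 32 |
| 3 | 27/30 = 90.0% | 27/27 = 100% | 27 / 33 |
| 5 | 25/30 = 83.3% | 25/25 = 100% | 25 / 35 |

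**Precision of a conversion rate counted as randomised** (exact Clopper-Pearson, two-sided 95%).

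- With x = 0 the upper limit is 1 - 0.025^(1/n): 16.8% for n = 20, 11.6% for n = 30, 8.8% for n = 40.
- With x > 0 the lower limit is the 2.5% quantile of Beta(x, n - x + 1), and the upper limit is the 97.5% quantile of Beta(x + 1, n - x). For 1/30 this gives 0.1% to 17.2%; for 3/30, 2.1% to 26.5%.

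**If the Introduction's 1% applied here.** The chance of at least one conversion is 1 - 0.99^n: 18.2%, 26.0% and 33.1% for n = 20, 30 and 40. At n = 30 the expected number is 30 × 0.01 = 0.3, and the chance of none is 74.0%.

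**The case against.** The strongest reply is that the transfer sentence is about care. It closes the paragraph on giving the epidural and may mean only that the patient then receives general anaesthesia. No text says such patients are analysed in Group B. This stands as far as it goes: the bias is conditional on how they are counted. But the plain reading is a move between arms, and no analysis set returns them to Group A.

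A reader might also infer that every failure is removed, so that Group A is fully feasible by construction. The documents do not support that. The rule names two triggers. An inadequate block, patient intolerance or a surgical reason falls outside it, although no outcome would record those either.

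Nor is it right to infer that the trial cannot report a conversion rate. The numbers allocated and transferred can both be counted. The plan does not commit to reporting the rate, which is a lesser fault.

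Feasibility is not defined, and blood gases, haemodynamics and the observation of complications all bear on tolerance of the technique. That is fair, but none of them says whether surgery was completed awake.

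Finally, 3 of 30 is ten times the only documented rate, and at 1% there may be nothing to distort. That is why the example is labelled an assumption. The 1% itself concerns conversion for the effects of paradoxical breathing, not all conversions, and the trial does not set out to confirm it.

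**Conclusion.** The point holds in conditional form. That feasibility has no outcome can be seen from the outcome list and needs no assumption. That Group A cannot show a failure for lasting haemodynamic instability or lasting hypoxaemia, and that the between-group comparison is biased, depends on transferred patients being counted in Group B. That is the plain reading, but the plan does not settle it.

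The size depends on a conversion count that the documents do not supply. Under the assumed 3 of 30, a 10% conversion rate would appear as 0 of 27. With no conversions there is no distortion, but the interval still reaches 8.8% to 16.8% depending on group size, so a bare statement of feasibility would mislead. The bias in the blood-gas comparison cannot be sized from the documents.

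The blood-gas comparison can still be carried out, so this is a gap to close before analysis rather than a fatal flaw.

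**What to change.** Add one outcome to the secondary list: *proportion of all patients allocated to Group A whose operation was completed under the epidural without conversion to general anaesthesia, with the reason for each conversion and an exact 95% confidence interval*. The denominator is everyone allocated to Group A, so conversions for any reason are counted, including those outside the two named triggers.

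Add one sentence to Statistical Analysis: patients who convert are counted and analysed, for every outcome, in the group to which they were randomised. Reword the transfer sentence so that it describes a change of anaesthetic and not a change of trial arm. The clinical triggers are not at issue and need no change.

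The cost is one outcome line, one case-report field and one sentence. Whether a patient converted will be known in theatre in every case. The small downside is that the reported feasibility, and any between-group difference, may look less favourable.

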## 3.METHODOLOGY:

### Patients and Methods:

- **Type of Study:** Prospective randomized clinical study.
- **Study Setting:** This study will be conducted in Ain Shams University Hospitals..
- **Study Period:** Expected for two years starting from 2019.
- **Study Population:**
  - Inclusion Criteria:*
    - ASA less than or equal II.
    - Age group: 21-65 years old.
    - The procedure expected to be completed within 2 hours.
  - Exclusion Criteria:*
    - Patients with expected difficult airway management.
    - Hemodynamically unstable patients.
    - Persistent cough or high airway secretions.
    - Severe Emphysema or clinical signs of active infectious disease.
    - Hypoxemia (PaO2 <60 mmHg) or hypercarbia (PCO2 >50 mmHg)
    - Coagulopathy (INR >1.5).
    - Obesity (BMI >30 Kg/m^2).
    - Infection at the injection site, allergy to local anesthetics.
    - Neurological disorders: seizures, intracranial mass or brain edema.
- **Sampling Method:** Randomized sampling by a computer generated random numbers table.
- **Sample Size:** 40 patients.

Sample size was calculated using PASS 11 program for sample size calculation and according to the (*Pompeo et al., 2004*) study, the mean PaO2 perioperatively in the awake group =  $-3 \pm 1.5$  mmHg and in the second group =  $-6.5 \pm 1.83$  mmHg. Sample size of 40 cases per group (total 40) can detect this difference with power 100% and  $\alpha$ -error 0.05.

- **Ethical Considerations:** Approval of the research ethical committee of faculty of medicine, Ain Shams University will be obtained and informed written consents will be taken from all the participants. The thoracic epidural placement will be performed by the most experienced person of the study team.

- **Study Tools:**

- **Anesthetic sheet.**

- **Visual analogue scale:** The Visual Analogue Scale (VAS) consists of a 10 cm straight line with the endpoints defining extreme limits of 'no pain at all' (0 cm) and 'pain as bad as it could be' (10 cm). The patient is asked to mark his pain level on the line between the two endpoints. The distance between 0 and the mark then defines the subject's pain score.

- **Anesthetic plan:**

In the anesthesia clinic, an informed written consent will be taken from every patient one day before the surgery. The VAS will be explained to the patients. Anesthesia will be provided according to the hospital protocol in respect to preoperative investigations, fasting hours and intra-operative monitoring and drugs.

- **Study Interventions:** The study will include 60 patients fulfilling the inclusion criteria. They will be randomized into 2 equal groups by a computer generated random numbers table, each consisting of 30 patients, namely group A and group B.

- **Group A:** Awake Patients will receive sole Thoracic Epidural Anesthesia.

- **Group B:** Patients will receive General Anesthesia with one lung ventilation.

Preoperatively, Intravenous access will be established and lactated ringer solution will be infused. Monitors for non-invasive blood pressure, heart rate, electrocardiogram (ECG), pulse oximetry (SpO2), and capnography for end tidal CO2 (ETCO2). Invasive arterial line is inserted for serial perioperative ABGs

Patients will be observed for any complications either related to the procedure e.g: hematomas or related to drugs injected e.g: hypotension, bradycardia, hypoxemia, nausea, vomiting or any other adverse effects and will be managed.

- In case of hypotension (drop of blood pressure >20% of baseline reading), 10-30mg of ephedrine diluted over 10ml normal saline 0.9% will be given intravenously by titration according to the blood pressure.
- In case of bradycardia, when it is associated with hypotension or any signs of impaired perfusion, 0.5mg of atropine will be given and can be repeated every 3-5min with a maximum of 3mg.
- In case of fall in peripheral SpO2, supplemental oxygen will be given to keep SpO2 above 94%.

- In case of postoperative nausea and vomiting (PONV), ondansetron 4mg diluted in 10ml normal saline 0.9% will be given intravenously slowly over 10 min.

Patients in thoracic epidural anesthesia (TEA) group will pre-medicated using midazolam 3-4 mg intravenous (IV) and fentanyl 50 mcg IV. Then patients will placed in the setting position. Under aseptic precautions, skin infiltration with local anesthesia will be done using a 5ml syringe containing 5ml of 1% lidocaine. An epidural catheter will be inserted between T3—T4 and T4—T5 for thoracic procedures meeting the inclusion criteria. A test dose (5 ml) of 2% lidocaine will be given, followed by 15-20 ml of bupivacain 0.5% and 50 mcg of fentanyl. The objective is to achieve sensory and motor block between C7 and T7 levels. At this level diaphragmatic respiration is maintained. In case of persistent hemodynamic instability or persistent hypoxemia, the patients will be transferred to the other group.

Patients will receive general anesthesia (GA) as follows, after proper assessment of the airway and anticipation of difficult airway, all patients will receive premedication in the form of 3-4 mg midazolam IV, ranitidine 50 mg IV as H2 receptor antagonist, metoclopramide 10 mg IV and dexamethasone 4 mg IV as post-operative nausea and vomiting (PONV) prophylaxis. Start preoxygenation with 100% O2 on 8 L/min for 3 min via face mask. Induction of anesthesia with propofol (2mg/kg) and fentanyl (1 mcg/kg). Tracheal intubation and double endotracheal tube insertion will be facilitated with cisatracurium 0.1 mg/kg. and confirmation of it is position will made by fiberoptic bronchoscopy, Anesthesia will be maintained with isoflurane (1-2 %) and cisatracurium (0.05 mg/kg per dose). After the end of the operation, anesthesia will be discontinued, and extubation of the patient will be done after full neuromuscular recovery after reversal of muscle relaxant by neostigmine (0.05 mg/kg) and atropine (0.02 mg/kg).

Postoperative pain and opioid consumption will be assessed after regaining of sensation using the VAS. Post-operative analgesia will be offered in regular doses of Paracetamol 1gm IV every 6 hours for the following 48 hours. Rescue analgesia will be given when VAS  $\geq$ 3, in the form of an injection of Pethidine 50 mg diluted in 10ml normal saline 0.9%, to be given intravenously slowly over 10 min.

- **Measured outcomes**

- **Primary outcome:**

Perioperative changes in blood gases [ Time Frame: Immediately before operation, intraoperatively per hour, and postoperatively per 2 hrs till 24h ]

Ratio of arterial oxygen tension to fraction of inspired oxygen (PaO2/FiO2), arterial carbon dioxide tension (PaCO2). Hypoxemia is defined as peripheral oxygen saturation (SpO2) < 92% on room air with a need for oxygen supplementation.

- **Secondary outcomes:**

- Postoperative pain using the Visual Analogue Scale (VAS), [ Time Frame: Postoperatively at 3h,12h and 24h ].
- Postoperative opioid (Pethidine) consumption [ Time Frame: Postoperatively during the 24h after regaining of sensation ].
- Hospital stay [ Time Frame: from day of operation to discharge; average, 5 days ]
- Perioperative changes in cardiocirculatory variables including heart rate (HR) and mean arteial pressure (MAP) [ Time Frame: Immediately before the operation, intraoperatively per hour, and postoperatively per 2 hrs till 24h ]
  - Bradycardia is defined as:  $HR \leq 50$  bpm
  - Hypotension is defined as a decrease in systolic blood pressure  $>20\%$  of basal.
  - Hypertension is defined as an increase insystolic blood pressure  $>20\%$  of basal.
- The onset of ambulence. Rate of occurence of falling after ambulence will be recorded in each group. [Time Frame: During the 24 hours after regaining of full motor power].
- Number of episodes of PONV [Time Frame: During the 24 hours postoperatively].
- **Statistical Analysis:** The collected data will be revised, coded and introduced to a PC using statistical package for social science (SPSS 15.0.1. for windows; SPSS Inc, Chicago, IL, 2001).
 

Data will be presented as mean and standard deviation (+- SD) for quantitative parametric data, median and range for quantitative non-parametric data and as numbers and percentage for qualitative data. Suitable analysis will be done according to the type of data obtained.  $P < 0.05$  will be considered significant.

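### The only power figure (100%) is for PaO2 in mmHg; the primary variables, PaO2/FiO2 and PaCO2, have no stated difference, SD or power

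*Combined protocol and SAP*

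**What the plan says.** The combined protocol and SAP contains one sample size calculation, under Sample Size in section 3 (Methodology). Citing a 2004 study of awake thoracoscopic resection, it takes "the mean PaO 2 perioperatively in the awake group" as -3 ± 1.5 mmHg and the second group as -6.5 ± 1.83 mmHg. It states that the sample "can detect this difference with power 100" percent at an alpha of 0.05. The text does not call these values changes, but negative values can hardly be anything else.

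The Primary outcome item is headed "Perioperative changes in blood gases", with sampling "Immediately before operation, intraoperatively per hour, and postoperatively per 2 hrs till 24h". The variables listed are "Ratio of arterial oxygen tension to fraction of inspired oxygen (PaO 2 /FiO 2 ), arterial carbon dioxide tension (PaCO 2"). No expected difference, SD or power appears for either. No time point or contrast is named as the one to be tested.

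The Statistical Analysis item sets P < 0.05 and leaves the choice of test to the type of data. It gives no rule for two primary variables.

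On inspired oxygen, Study Interventions says that if saturation falls "supplemental oxygen will be given to keep SpO 2 above 94" percent. The general anaesthesia group is preoxygenated with 100% O2. Section 3 also says "Anesthesia will be provided according to the hospital protocol" for intra-operative monitoring and drugs; that hospital protocol is not part of the documents.

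**The concern.** A sample size is justified when its power refers to the variable that decides the trial. Here the calculation uses PaO2 in mmHg, while the trial is to be judged on PaO2/FiO2 and PaCO2. The plan does not say what difference in either variable it is designed to detect.

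This matters most if the result is null. A reader who sees 100% power may take a non-significant PaCO2 or PaO2/FiO2 result as proof that no relevant difference exists, and the plan gives no basis for that. PaCO2 is not peripheral: the Introduction names hypercapnia as a risk of the awake technique and discusses postoperative PaCO2 relative to conventional anaesthesia.

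**Working it through.** **Inputs.** From Sample Size: difference = -3 - (-6.5) = 3.5 mmHg; SDs 1.5 and 1.83; alpha 0.05 (two-sided assumed). The group size is given inconsistently: 40 in total and also 40 per group under Sample Size, and 30 per group under Study Interventions. I therefore use n = 20, 30 and 40 per group throughout.

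**Step 1: reproduce the stated figure.** Pooled SD = √((1.5² + 1.83²)/2) = √(5.5989/2) = 1.673. Standardised difference d = 3.5/1.673 = 2.092. For a two-sample t-test the noncentrality is d·√(n/2), with 2n - 2 degrees of freedom.

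| n per group | noncentrality | power |
|---|---|---|
| 20 | 6.62 | 0.999996 |
| 30 | 8.10 | > 0.99999999 |
| 40 | 9.36 | > 0.99999999 |

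The 100% is correct for PaO2 at every group size the documents could mean.

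**Step 2: does it transfer to the primary variables?**
- PaCO2: no input to the calculation concerns it, so nothing transfers.
- PaO2/FiO2: if FiO2 were a constant c, difference and SD would both be divided by c. Then d = (3.5/c)/(1.673/c) = 2.092, unchanged, and the 100% would carry over. If FiO2 differs between patients, times or groups, the SD and the mean difference of the ratio both depend on how it varies, and the documents do not give that. Oxygen added when saturation falls makes FiO2 depend on the patient's course, and one group is preoxygenated with 100% O2.

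**Step 3: what power could be.** No power can be computed in the primary variables' own units. Over a range of assumed standardised effects (one variable, one time point, unadjusted two-sided t-test, alpha 0.05):

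| assumed effect | n = 20 | n = 30 | n = 40 |
|---|---|---|---|
| 0.5 SD | 0.34 | 0.48 | 0.60 |
| 0.8 SD | 0.69 | 0.86 | 0.94 |
| 1.05 SD (half of 2.09) | 0.90 | 0.98 | 0.996 |

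**Step 4: detectable effect for a single primary variable**, in SDs of the change score, same assumptions:

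| power | n = 20 | n = 30 | n = 40 |
|---|---|---|---|
| 80% | 0.91 | 0.74 | 0.63 |
| 90% | 1.05 | 0.85 | 0.73 |

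**Step 5: two primary variables.** If a significant result on either variable counts as success and each is tested at 0.05, the false-positive risk is 1 - 0.95² = 0.0975, about 9.8%, for independent variables at one time point each. Repeated sampling can add to this. A procedure lasting the full two hours gives 1 + 2 + 24/2 = 15 samples; shorter procedures give fewer.

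The two possible rules can be compared on one basis, the power of the trial as a whole (independent variables, equal effects):
- Either suffices, alpha 0.025 each: 80% trial-level power needs per-variable power 1 - √0.20 = 0.553; 90% needs 1 - √0.10 = 0.684.
- Both required, alpha 0.05 each: 80% needs √0.80 = 0.894; 90% needs √0.90 = 0.949.

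| rule | n = 20, 80% (90%) | n = 30 | n = 40 |
|---|---|---|---|
| either | 0.78 (0.89) SD | 0.63 (0.72) | 0.54 (0.62) |
| both | 1.04 (1.17) SD | 0.84 (0.94) | 0.73 (0.81) |

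Positive correlation between the variables would raise the requirement under the first rule and lower it under the second.

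**The case against.** The strongest reply is that the calculation is not foreign to the primary outcome. PaO2 is a blood gas, the outcome is headed as changes in blood gases, and PaO2 is the numerator of the first listed variable. The stated effect is also very large, so there is margin: half of it would still give about 0.90 power at 20 per group. FiO2 at sampling may be governed by the hospital protocol, which is not in the documents.

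Much of this stands. For PaO2/FiO2 it would be too strong to say that the 100% is uninformative; the accurate statement is that its transfer is not shown. The margin is real, but it holds only if the effect on the primary variable is at least that large, and no document says so. None of the reply reaches PaCO2.

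Three stronger readings are tempting and are not supported:
- That the trial is underpowered. Without a difference and SD for the primary variables, low power cannot be shown any more than high power can.
- That the 100% is a miscalculation. It reproduces.
- That the outcome text itself shows FiO2 to vary at blood-gas sampling, because it says "on room air with a need for oxygen supplementation". That phrase belongs to the definition of hypoxemia by SpO2 and does not describe sampling conditions.

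**Conclusion.** The point holds. The only power statement concerns PaO2 in mmHg. PaCO2 has no power basis, and for PaO2/FiO2 the basis is related but depends on a constant FiO2 that the plan does not ensure. Power for the primary outcome is unsupported, not shown to be low.

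That no difference, SD or power is given for the primary variables rests on the text alone. The detectable effects assume one variable at one time point and an unadjusted two-sided t-test. The two-variable figures also assume independence and equal effects. The 9.8% applies only if success on either variable counts, which the plan neither states nor excludes. The conflicting group sizes are a separate matter and do not change this conclusion. This should be corrected before the analysis, but it is not evidence that the trial cannot answer its question.

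**What to change.** 1. Name one primary variable and one time point or summary contrast. If both variables stay primary, state the rule: either may succeed at alpha 0.025 each, or both must succeed at alpha 0.05 each.
2. Restate power for that variable from a sourced difference and SD of the change. For example: *For the change from the pre-operative value in [variable] at [time point], [source] gives an expected difference of [x] and an SD of the change of [y]; [n] per group gives [z]% power (two-sided t-test, alpha 0.05).*
3. If no source exists, say so, limit the 100% to PaO2, and state the single-variable detectable effect from Step 4 for the group size the sponsor confirms. This shows what could be detected, not that such an effect is expected.
4. If a two-variable rule is chosen, report trial-level power on the same basis for whichever rule applies, as in Step 5. Power for each variable at alpha 0.025 is not the trial's chance of success under the either rule and should not be reported as such.
5. Confirm against the cited study that -3 and -6.5 are changes.

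The cost is a few sentences and a search for a source. The stated power becomes less favourable than 100%. No extra patients are requested; the sample size would come into question only if a sourced effect proved smaller than the detectable one.

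### The planned sample size is given as 40 and as 60, and the stated 100% power neither settles which is meant nor is shown for the primary outcome

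*Combined protocol and SAP*

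**What the plan says.** Section 3 of the combined protocol and SAP gives the size of the trial in two places.

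- **Sample Size item.** The headline figure is 40 patients. The justification then reads "Sample size of 40 cases per group (total 40) can detect this difference with power 100" per cent, with alpha 0.05 and no statement of sidedness. The planning figures, attributed to a published study, are described as the mean PaO2 "perioperatively in the awake group" and in the second group: -3 ± 1.5 and -6.5 ± 1.83 mmHg.
- **Study Interventions item.** "The study will include 60 patients fulfilling the inclusion criteria", randomised into two equal groups, "each consisting of 30 patients, namely group A and group B".

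The primary outcome is headed "Perioperative changes in blood gases", measured before the operation, hourly during it and every two hours afterwards to 24 hours. The variables listed are "Ratio of arterial oxygen tension to fraction of inspired oxygen" and arterial carbon dioxide tension. The Statistical Analysis item names no test: "Suitable analysis will be done according to the type of data obtained".

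**The concern.** There are two linked problems.

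First, the enrolment target is not defined. The Sample Size item contradicts itself and also disagrees with the Study Interventions item. If enrolment ends at 40, a reader cannot tell whether the plan was met or fell 20 short of 60, which is one third of that target.

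Second, the 100% figure reads as the power of the trial, but it is computed on a quantity that is not one of the two named primary variables. A reader could take a null result on PaO2/FiO2 or PaCO2 as near-conclusive when the documents give no basis for that.

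**Working it through.** **Step 1. Set the stated sizes side by side (two equal groups).**

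| Place | Stated | Implied per group | Implied total |
|---|---|---|---|
| Sample Size, headline | 40 patients | 20 | 40 |
| Sample Size, justification, total | 40 | 20 | 40 |
| Sample Size, justification, per group | 40 | 40 | 80 |
| Study Interventions | 60, as 2 × 30 | 30 | 60 |

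The totals actually written are 40 and 60, a gap of 20. The figure 80 is never written. It arises only if the per-group wording is taken literally and the adjoining total is discarded.

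**Step 2. Reproduce the stated power.** The inputs are those of the Sample Size item. Sidedness is not stated, so two-sided is assumed.

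- Difference: -3 − (-6.5) = 3.5 mmHg
- Root-mean-square SD: √((1.5² + 1.83²)/2) = √((2.25 + 3.3489)/2) = 1.673 mmHg
- Standardised difference: d = 3.5/1.673 = 2.09
- Two-sample t-test with n per group: noncentrality d√(n/2) on 2n − 2 degrees of freedom

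| n per group | Total | Noncentrality | Power, two-sided 0.05 |
|---|---|---|---|
| 5 | 10 | 3.31 | 82.5% |
| 6 | 12 | 3.62 | 90.3% |
| 10 | 20 | 4.68 | 99.30% |
| 11 | 22 | 4.91 | 99.65% |
| 14 | 28 | 5.53 | 99.96% |
| 20 | 40 | 6.61 | 99.9996% |
| 30 | 60 | 8.10 | above 99.9999% |
| 40 | 80 | 9.35 | above 99.9999% |

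The stated 100% is reproduced to rounding. Allowing unequal SDs (Welch test) also gives 99.9996% at 20 per group, and a one-sided test at 20 per group gives 99.9999%.

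**Step 3. Ask whether the power identifies N.** It does not. Two-sided, every size from 11 per group upward rounds to 100%, so the figure is equally consistent with 20, 30 and 40 per group.

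**Step 4. Compare the planning variable with the primary outcome.** The planning figures are labelled mean PaO2 but are negative, so they appear to be changes. The documents do not say from what baseline or to what time. The primary variables are PaO2/FiO2 and PaCO2 at repeated times. PaO2 is the numerator of the first, but a difference and SD in mmHg do not carry over to a ratio, or to PaCO2. Without an expected difference and SD for either variable, power cannot be computed in either direction.

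**Step 5. Show what can be said without an SD.** Solving the same t-test for the difference detectable with 80% power, in SD units of any single continuous variable:

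| n per group | Detectable difference |
|---|---|
| 20 | 0.91 SD |
| 30 | 0.74 SD |
| 40 | 0.63 SD |

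These assume one two-sided test at 0.05 on one variable, with no loss and no movement between groups. The plan does foresee movement: for awake patients with persistent instability or hypoxaemia it says "the patients will be transferred to the other group". The Sample Size item makes no allowance for it.

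**The case against.** The strongest reply is that there is only one real conflict, 40 against 60. The Sample Size item gives 40 twice as a total, so the per-group wording is probably a slip, and the Study Interventions item is complete and internally consistent. On the protocol's own inputs the choice hardly matters, because power is essentially 100% at either size, and the 100% is not an arithmetic error. PaO2 is itself a blood gas, and negative values fit a change score, so a mismatch with the primary outcome is not proven. The detectable differences are generic to any two-group t-test. Finally, naming a primary variable and time point is more than a change of wording.

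Much of this is fair. The 100% is correct for the inputs given, 80 is not a stated target, and the documents support only that power for the primary variables is not shown. They do not support a claim that the trial is underpowered. But correcting the slip in the Sample Size item still leaves 40 against 60. The choice is immaterial only if a 2.09 SD effect applies to the primary variable, which the plan does not establish. The detectable differences are indeed generic. They are offered because nothing more specific can be computed. The point about the effort involved is accepted and reflected in the cost below.

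**Conclusion.** The concern holds and must be fixed. The plan states two different totals, 40 and 60, and one impossible combination, with nothing to say which governs. This follows from the text alone.

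The 100% power is right to rounding for a 3.5 mmHg difference with SDs of 1.5 and 1.83, but it fits 20, 30 and 40 per group equally. It is not shown for PaO2/FiO2 or PaCO2. Whether the true power for those variables is high or low cannot be determined from the documents.

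The calculations take the planning figures as quoted, because the cited study was not available, and assume a two-sided t-test with equal allocation. The documents do not show which N was intended.

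**What to change.** 1. State one total and one per-group number, identically in the Sample Size and Study Interventions items: [N] patients in total, [N/2] per group.
2. State from the cited study what variable and time point the figures -3 ± 1.5 and -6.5 ± 1.83 mmHg describe.
3. Stop presenting 100% as the power for the primary outcome unless those figures are shown to apply to it.
4. Name the primary variable, and the time point or summary over time, to which the power statement refers. Give the power with its assumed difference, SD, test and sidedness. If no SD is available, say so and give the detectable difference at 80% power for the chosen N, with the conditions listed in the working.

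**Cost.** Items 1 to 3 are text changes. Item 4 needs a decision on the primary variable and time point, and power for it must then be restated or declared unknown. The fix imposes no particular N and by itself requires no extra enrolment. If recruitment has been working to 40 and the sponsor confirms 60, the additional 20 patients follow from what the plan already says.
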